### **I. BACKGROUND AND SIGNIFICANCE**

Depression and cardiovascular disease (CVD) frequently occur together, exacerbate each other, and when combined, are among the leading causes of disability and death. Compared to people without depression, those with **depression have two times the risk of myocardial infarction, and are four times more likely to die from coronary heart disease**. Mostly because of cardiovascular comorbid conditions, people with major depressive disorder (lifetime prevalence of about 17%), or bipolar disorder (prevalence of about 4.5%) die 8 to 25 years earlier than the general population. **Conversely, people with CVD (overall prevalence over 33% of adults) have three to four times the rate of depression compared to the general population**, and die at twice the rate if they have comorbid depression compared to those without depression. Depression and CVD interact in a vicious cycle and are responsible for a large proportion of morbidity and mortality.

**Why Exercise may be the key to breaking the vicious cycle: The impact of exercise on CVD is clear and clinically meaningful.** Exercise improves virtually all risk factors for CVD as well as the disease itself. For example, exercise positively benefits hypertension as well as risk of metabolic syndrome and diabetes. A walking study of 8,436 male and 33,586 female participants found that this physical activity remarkably lowered the risk of CVD mortality by 35%, ischemic heart disease mortality by 31%, diabetes mortality by 91%, and 34% for hypertensive diseases. Recently, a 15-year study investigating the role of exercise in preventing and treating CVD in healthy adults (N=8,662) found that people exercising regularly were 0.35 (0.13–0.98) times less likely to die from CVD compared to those not exercising regularly. Given these data the US Preventive Services Task Force (USPSTF) recently published a guideline recommending *“referring adults who are overweight or obese and have additional CVD risk factors to intensive behavioral counseling interventions to promote a healthful diet and physical activity for CVD prevention.”*

**The impact of exercise on depression is also clear and clinically meaningful.** Two recent meta-analyses found that exercise for depression was superior to no treatment at all as well as to similarly efficacious psychotherapies. The treatment effect size for exercise across 11 well controlled trials was large (Hedge’s  $g = 1.39$ , for a random effects analyses), indicating that it has powerful antidepressant properties. Exercising 3 days/week for 45-min over four months is as effective in reducing depressive symptoms as an antidepressant (i.e., sertraline) for individuals with unipolar depression. Other studies have found that exercise improves bipolar depression, one’s stress reactivity and cognition. Similar to the risk for CVD, there is a dose-response relationship between exercise and depression highlighting the direct impact of exercise on one’s mental health. Exercise may also address the underlying mechanisms for the vicious cycle of depression and CVD. Recent evidence suggests that depression is linked to inflammatory processes (indicated by C-reactive protein and interleukins) and inflammation is a key feature of

atherosclerosis and CVD. The most robust way to combat inflammation is to exercise. In sum, exercise is key to reducing the impact of these co-occurring conditions, which increases morbidity and mortality in the US population. **It is less clear, however, how to best help people make this important behavioral modification.**

**The proposed study is particularly poised to further target high-risk populations as individuals with lived experience of depression and/or heart disease will co-design two online interventions with clinicians and researchers.** We will also leverage existing knowledge about facilitating exercise amongst people with depression and individuals who are at risk for, or have, CVD online, through the positive role of others (e.g., online communities) and utilizing the rich experience of the field of online education to keep people engaged in the two chosen web-based, empirically-validated interventions to enhance exercise. The proposed study also seeks to disseminate two targeted, empirically-based interventions for individuals with depression at risk for or with CVD. By bringing together MoodNetwork and Health eHeart (UCSF, CHR #12-09993), we have the immediate opportunity to serve the participants currently enrolled in our two networks (>4100 in MoodNetwork and >80,000 in Health eHeart) across 50 states, 5 territories, and 33 countries. Potential dissemination, however, is much wider. Thus, **the impact of this study is increasing access to empirically-supported treatments that are specifically tailored by partnering with patients to enhance exercise in depressed individuals who are at risk for, or have, CVD.**

**This study will utilize the National Institutes of Health-funded Eureka mHealth Research Platform (UCSF, CHR #16-19397),** a platform that enables investigators to conduct mobile, online, and wireless health research in a less costly, more streamlined manner, in order to recruit participants, collect and store study data, and manage study participants. The research platform will accelerate our ability to access a large cohort of volunteers who have agreed to participate in research, and provide a quick, affordable means for collecting their health data through mobile and wireless technologies.

## II. SPECIFIC AIMS

The purpose of this research is to compare the effectiveness of web-based cognitive behavior therapy (CBT) and use of a fitbit device, web-based mindfulness-based cognitive therapy (MBCT) and use of a fitbit device, and use of a fitbit device with no adjunctive therapy for increasing physical activity in people with a history of depression and who have or are at risk of having cardiovascular disease.

### A. Primary Aims

**Aim 1: To determine if 1) web-based CBT or web-based MBCT, supported by use of Fitbit technology for self-tracking of activity, improves physical activity, and 2) How these two therapies compare to a Fitbit-only control group.**

*Hypothesis 1a:* Because CBT (compared to MBCT) is the more directive intervention, we hypothesize that CBT will be superior to MBCT in increasing daily steps over the course of 8-weeks of treatment and at follow-up.

*Hypothesis 1b:* Both forms of therapy-based treatment will be superior to the Fitbit only control group in increasing daily steps over the course of 8-weeks of treatment and at follow-up.

**Aim 2: Explore the heterogeneity of treatment effects (HTE) to both interventions.**

This aim will allow us to *explore* who will benefit from either CBT+ Fitbit, MBCT+ Fitbit, or Fitbit alone (predictors) and to determine the factors that can help match patients to each intervention (moderators or who will have better outcomes with CBT+Fitbit, MBCT+Fitbit, or Fitbit only).

**III. INTERVENTION MODULES AND OVERVIEW**

Participants in both therapy-based interventions will access materials (e.g., client vignettes, videos, activities) that illustrate ways to increase physical activity (e.g., walks, runs, climbing stairs, etc.). They will be guided to gradually increase their daily steps (physical activity) at their own pace. Both CBT and MBCT will be provided online and will guide participants through the elements of each treatment which are geared to address the barriers against exercise that individuals with mood disorders at risk for or with CVD face (fear of the physiological signs of exertion as they may mean a heart attack, etc.). Besides structured guidance towards exercise, the main focus of both treatments will be on addressing these obstacles that prevent individuals from engaging in exercise. Participants in both of these groups will receive Fitbit devices to measure their steps (main outcome) throughout the study. In addition to the two treatment-based intervention group there will also be a group of participants who serve as controls. This group will receive a Fitbit device, but no form of therapy and will not have access to the online therapy material. By including this control group, we will be able to ensure that any treatment effect is not due to wearing a Fitbit.

**Cognitive-behavioral therapy (CBT):** CBT will be based on previous work using CBT to enhance exercise in individuals with mood disorders which includes the following elements: (1) identifying and setting realistic exercise-based goals and intermediate goals (to maximize success to increase motivation); (2) behavioral scheduling to optimize when to exercise, identify rewards for exercising, and problem solve obstacles to exercising; and (3) identify dysfunctional, maladaptive thoughts about exercise (which decrease motivation) and skills to identify more adaptive, positive thoughts (to overcome thoughts of being too tired or too stressed to exercise). These aspects follow the core components of CBT, or to change dysfunctional thoughts and behaviors to change a problem behavior (i.e., sedentary behavior). Evidence shows that adjunctive CBT for exercise helps patients improve their planning to exercise, motivation to exercise, and self-efficacy (or one's belief in their ability) to exercise. Two hundred participants will be randomized to this group.

The CBT Program can be added to an individual's regular course of treatment (such as medications), but should not replace ongoing treatment with his/her own doctor. Throughout participation in this study, the participant should continue any medications or treatments that his/her own doctor feels will best treat the symptoms of depression and/or cardiovascular disease.

**Mindfulness-based Cognitive Therapy (MBCT):** MBCT will be based on previous work with individuals with mood disorders . A central aspect of MBCT is the concept of awareness. Participants practice a variety of meditation types (e.g. breath awareness) and learn to bring mindfulness to everyday situations. Awareness will be directed to elements in participants' lives that interfere with living a more productive, physically active life (e.g. thoughts and feelings that interfere with becoming more physically active; stressful situations and circumstances that prevent them from engaging in exercise). The program guides participants to a mindful consideration about how to "respond" to factors that interfere with a healthy lifestyle. In addition participants bring mindfulness to actual physical activity and the pleasant after effects (to enhance motivation). Compared to CBT, mindfulness, takes a more explorative, self-guided approach of raising awareness rather than a more directive and prescriptive approach adopted by CBT. The fundamental difference between CBT and MBCT is that CBT focuses on goal setting, planning, behavioral contingencies and re-conceptualizing of dysfunctional thoughts that interfere with goal achievement, whereas MBCT strives for gradually increasing awareness towards personal and situational factors that interfere with a healthy, more physically active lifestyle, and developing personalized ways to respond to these factors as well as changing the experience of exercise itself. Although participants cannot choose the intervention, we will explore treatment preferences as a potential source of heterogeneity effects. Two hundred participants will be randomized to this group.

The MBCT Program can be added to an individual's regular course of treatment (such as medications), but should not replace ongoing treatment with his/her own doctor. Throughout participation in this study, the participant should continue any medications or treatments that his/her own doctor feels will best treat the symptoms of depression and/or cardiovascular disease.

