Accessed through a links managed by MoodNetwork.org and Health-eHeart.org, interested participants will sign an online consent form waiver, found in a web portal hosted by the Eureka mHealth Research Platform. Eureka is a multi-tenant system (architecture in which a single instance of a software application serves multiple customers), which is housed on a HIPAA compliant Amazon cloud database. Once the participant has read and electronically signed the waiver of consent form, participants will register for Eureka and then complete a short battery of assessments to determine eligibility. The assessments will consist of 3 standard psychological assessments (The Patient Health Questionnaire [PHQ-9], the Altman Self-Rating Mania Scale [ASRM], and the Mini International Neuropsychiatric Interview [MINI], and 2 cardiac health assessments (The Duke Activity Status Index [DASI], and the International Physical Activity Questionnaire [IPAQ]). They will also be asked to complete a standard demographic form, and their medical and psychiatric histories. If they are not eligible, they will be thanked for their interest and informed that unfortunately, they are not eligible. If found eligible, they will provide their mailing address information so that we can ship them a Fitbit device. Once they receive their Fitbit device, they will return to the study portal to sync their fitbit with our system so that we can collect their step data complete a series of questionnaires, including the World Health Organization Composite International Diagnostic Interview for Bipolar Spectrum Disorders (CIDI), The Patient Health Questionnaire (PHQ-9), The Altman Self-Rating Mania Scale (ASRM), The Sheehan Disability Scale (SDS), The World Health Organization-5 Well-Being Index (WHO-5), the Self Efficacy for Exercise (SEE), the International Physical Activity Questionnaire (IPAQ), the Seattle Angina Questionnaire-7 (SAQ-7) and the Perceived Stress Scale (PSS). Once completed, participants will be randomized to CBT + Fitbit, MBCT + Fitbit, or the Fitbit-only control group. Those who are randomized to one of the two therapy-based treatment groups will be sent to a portal on MoodNetwork.org to access the interventions. Those randomized to the Fitbit-only treatment group will be brought to a page thanking them for their participation, reminding them to wear their fitbit for the next 16 weeks, and informing them that they will be emailed reminders when they need to return to the portal to complete surveys. All participants, regardless of study group, will be asked to return to Eureka in weeks 2, 4, 6, 8, and 16 to complete a battery of assessments and asked questions about adverse events that may have occurred since beginning the study (detailed in Table 1 below).

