**Table 1. Schedule of Assessments**

Weeks	0	1	2	4	6	8	16
	Pre				Mid	Post	Follow-Up
Demographics	X						
Medical/Psych Hx	X						
Mini International Neuropsychiatric Interview (MINI)	X						
World Health Organization Composite International Diagnostic Interview for Bipolar Spectrum Disorders (CIDI)		X					
Duke Activity Status Index (DASI)	X						
The Patient Health Questionnaire (PHQ-9)	X	X	X	X	X	X	X
Altman Self-Rating Mania Scale (ASRM)	X	X	X	X	X	X	X
Sheehan Disability Scale (SDS)		X		X		X	X
Well-Being Index (WHO-5)		X	X	X	X	X	X
Perceived Stress Scale (PSS)		X		X		X	X
Self Efficacy for Exercise (SEE)		X					

International Physical Activity Questionnaire (IPAQ) short form	X	X					
Cardiac Events	X	X	X	X	X	X	X
Seattle Angina Questionnaire – 7 (SAQ-7)*		X				X	X
Adverse Event Questions			X	X	X	X	X

\*The SAQ-7 will only be re-administered to those who respond affirmatively to having angina (coronary artery disease), heart attack, coronary bypass surgery coronary stent or angioplasty procedure or if participant has recurrent chest discomfort with activity that goes away within 10 minutes of rest or with nitroglycerin

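### The plan promises to explore treatment preference as a source of heterogeneity, but lists no preference item before randomisation and no model that would use one

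*Combined protocol and SAP*

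**What the plan says.** The commitment is in the MBCT paragraph of Section III: "Although participants cannot choose the intervention, we will explore treatment preferences as a potential source of heterogeneity effects". It fits Aim 2 in Section II, which sets out to "determine the factors that can help match patients to each intervention".

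The Overview of Section IV describes data collection up to randomisation in two steps. Screening uses the PHQ-9, ASRM, MINI, DASI and IPAQ, and adds: "They will also be asked to complete a standard demographic form, and their medical and psychiatric histories". After the Fitbit arrives, a second battery follows: CIDI, PHQ-9, ASRM, SDS, WHO-5, SEE, IPAQ, SAQ-7 and PSS. Then: "Once completed, participants will be randomized to CBT + Fitbit, MBCT + Fitbit, or the Fitbit-only control group".

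The next step shows participants their arm. For the therapy arms: "Those who are randomized to one of the two therapy-based treatment groups will be sent to a portal on MoodNetwork.org to access the interventions". For the controls: "Those randomized to the Fitbit-only treatment group will be brought to a page thanking them for their participation".

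The Aim 2 text in Section VIII.B gives between-group effect sizes with confidence intervals, and Mann-Whitney comparisons of the arms on FRS and on change in PHQ-9, ASRM and SDS.

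**The concern.** A moderator analysis needs a variable measured before allocation and a model in which that variable interacts with arm. For treatment preference the plan lists neither.

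Timing makes the first gap the more serious. A missing model can still be written before the data are analysed. A missing baseline variable cannot be recovered once participants know their arm. A preference stated after that may reflect satisfaction or disappointment with the allocation, so it could differ between arms because of the allocation itself. It would then no longer be a baseline characteristic on which the randomised arms can be compared.

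At stake is an exploratory question that the protocol says it will address. Neither Aim 2 nor its analysis text names a candidate moderator, so preference is the only source of heterogeneity that the protocol commits to in specific terms.

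**Working it through.** **1. Promise against collection.** Each place where a preference item could appear was compared with the Section III sentence.

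| Place | Content | Preference item named? |
|---|---|---|
| Section IV, Overview: screening | PHQ-9, ASRM, MINI, DASI, IPAQ, demographic form, histories | No |
| Section IV, Overview: battery before randomisation | CIDI, PHQ-9, ASRM, SDS, WHO-5, SEE, IPAQ, SAQ-7, PSS | No |
| Section IV.c: instrument descriptions | The scales above, plus Cardiac Events and the adverse event questions | No |
| Table 1 | 15 rows over 7 time points (weeks 0, 1, 2, 4, 6, 8, 16) | No, in any row or week |

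**2. Promise against analysis.** The Aim 2 text in Section VIII.B compares arms overall. It has no preference variable and no interaction term. Adding the item alone would therefore not deliver the analysis.

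**3. Order of events.** Second battery, then randomisation, then the therapy portal or the control page. The documents do not use the word unblinded, but this routing makes the arm plain to the participant at once. The last point at which a clean preference can be recorded is the week 1 battery.

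**4. What the analysis could detect if the item were added.** The plan's own derived figure comes first: Sections VIII and VIII.D give a Bonferroni level of 0.0008 for 61 secondary and exploratory analyses. 0.05/61 = 0.00082, which rounds to 0.0008, so the figure reproduces. Section VIII.B also says that each test uses a two-tailed 0.05, so both levels are shown.

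Inputs from the documents: 200 per therapy arm (Section III) and 20% attrition (Section VIII.C), giving 200 × 0.8 = 160 per arm.

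Assumptions, because the documents give no effect size, SD or preference split: a binary preference with share p from 0.5 to 0.2, the same in both arms; a simple comparison of CBT with MBCT on a continuous outcome; 80% power.

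Standard error of the preference-by-arm interaction in SD units: SE = √(2/(np) + 2/(n(1−p))).
Detectable interaction = (z for two-sided alpha + z for 80% power) × SE, where the sum in brackets is 1.960 + 0.842 = 2.802 at alpha 0.05 and 3.353 + 0.842 = 4.194 (before rounding) at 0.0008.

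- n = 160, p = 0.5: SE = √(2/80 + 2/80) = 0.224
- n = 160, p = 0.2: SE = √(2/32 + 2/128) = 0.280

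| n per therapy arm | p | Detectable at 0.05 | Detectable at 0.0008 |
|---|---|---|---|
| 160 | 0.5 | 0.63 SD | 0.94 SD |
| 160 | 0.2 | 0.78 SD | 1.17 SD |
| 200 | 0.5 | 0.56 SD | 0.84 SD |
| 200 | 0.2 | 0.70 SD | 1.05 SD |

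With 160 per arm, power for an interaction of 0.5 SD is 61% (p = 0.5) to 43% (p = 0.2) at alpha 0.05, and 13% to 6% at 0.0008.

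**The case against.** The strongest objection is that the lists are not exhaustive. The Overview introduces the second battery in open-ended terms and omits Cardiac Events, which Table 1 schedules at weeks 0 and 1. The content of the demographic and history forms is not reproduced. Eligibility items such as pregnancy and current use of an activity monitor have no row in Table 1, and weight and FRS are analysed in Section VIII.B without one. A preference item could sit in an unlisted form. This stands as a limit on certainty. A reader might infer that the analysis is impossible, or that none of the 500 participants would have a baseline preference value. The documents support only that no such item is listed. Nothing in them suggests an unlisted one; if it exists, adding it to Table 1 settles that part of the point.

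A second objection is that the promise is one clause in an intervention description, worded as exploration, and that the Aim 2 text does not repeat it. That is fair and limits the importance of the point. A reader might also infer that unmeasured preference biases the main result. The documents do not support that: Hypothesis 1a is a randomised comparison and does not use preference. They also contain no evidence that a mismatch between wanted and received arm drives wear, dropout or mood in this trial.

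A third objection is low yield, and the figures confirm it. That argues for reporting estimates with intervals rather than relying on a significance test. It does not reconcile a promise with the absence of a variable.

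**Conclusion.** The point holds as an inconsistency between a stated exploratory analysis and the listed data and model. From the data the plan says it collects, preference cannot be examined as a moderator, and asking after allocation would not repair this. The finding comes from reading the sections together and does not depend on the power figures. Those are an illustration under assumed preference shares and a simplified two-arm contrast. They show that only a large interaction, about 0.63 SD or more at alpha 0.05 after attrition, would be detected with 80% power.

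The change is worth making because it is cheap and can only be made before a participant is randomised. It has no bearing on the validity of the primary comparison.

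**What to change.** 1. Add one item to the week 1 battery, completed before the randomisation step. It should describe the arms neutrally and offer CBT + Fitbit, MBCT + Fitbit, Fitbit only, or no preference. Add it to the Section IV Overview and as a row in Table 1.
2. Add to the Aim 2 text in Section VIII.B an exploratory interaction between stated preference and randomised arm, reported as estimates with confidence intervals. Do not use a matched/unmatched variable: match depends on the allocated arm as well as on preference, so it is not a baseline characteristic, and it is undefined for people with no preference.
3. Count the analysis among the 61 secondary and exploratory analyses. If it is an addition, 0.05/62 = 0.00081, which still rounds to 0.0008.
4. Leave anyone already randomised as missing and do not ask them in retrospect.

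The cost is one survey question on the existing platform, a few seconds of burden, and amendments to the Overview, Table 1 and Aim 2. Asking may make disappointment with the allocation more salient, and power will be low.

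If the sponsor prefers not to collect the item, deleting the Section III sentence also resolves the inconsistency.
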